2.1.2 Prior or concomitant medications

All medications taken from the signed informed consent date up to the first study treatment administration and until the end of the study (ie, 30 days after the end of treatment) are to be reported in the case report form pages.

All medications will be coded using the World Health Organization-Drug Dictionary (WHO-DD), using the version currently in effect at Sanofi at the time of database lock.

- Prior medications are those the patient used prior (<) to first study treatment administration. Prior medications can be those discontinued before first administration or those ongoing during the treatment phase.
- Concomitant medications are any treatments received by the patient concomitantly to the study treatment from first administration to the last administration +30 days. A given medication can be classified both as a prior medication and as a concomitant medication.

Any technical details related to computation, dates, imputation for missing dates are described in [Section 2.5.3](#).

2.1.3 Efficacy /pharmacodynamics endpoints

2.1.3.1 Primary endpoint(s)

The primary endpoint is the percentage reduction in Ki67 level after a 14-day treatment period compared to baseline. Ki67 level is expressed in terms of percentage of positive tumor cells tested by immunohistochemistry [IHC]) and will be recorded independently by 2 histopathologists. A single Ki67 result derived by the antilog transformation of the mean of the log of 2 reported values, will be used for calculation. The inter-reader variability in reporting Ki67 values will be

assessed during the trial, and a third adjudicator might be involved if the agreement between two Ki67 values does not meet the pre-specified criteria (see [Section 2.4.5.1.1](#)).

The primary endpoint is calculated as: $100 \times (\text{Ki67}_{\text{pre}} - \text{Ki67}_{\text{post}}) / \text{Ki67}_{\text{pre}}$, where Ki67_{pre} and $\text{Ki67}_{\text{post}}$ are used to denote the pre-treatment and post-treatment Ki67 values respectively. Since both SAR439459 and letrozole treatments intend to reduce Ki67 levels, a positive result is expected with this formula and denoting Ki67 value reduction.

2.1.3.2 Secondary endpoint(s)

Secondary efficacy endpoints are defined below.

- The proportion of participants with relative decrease from baseline in Ki67 $\geq 50\%$ (ie, $100 \times (\text{Ki67}_{\text{pre}} - \text{Ki67}_{\text{post}}) / \text{Ki67}_{\text{pre}} \geq 50\%$) as tested by IHC after a 14-day treatment period compared to baseline.
- Change in ER expression H-Score after a 14-day treatment period. This endpoint is calculated as $\text{H-score}_{\text{post}} - \text{H-score}_{\text{pre}}$, where $\text{H-score}_{\text{post}}$ and $\text{H-score}_{\text{pre}}$ are used to denote the post- and pre-treatment H-scores respectively.

2.1.3.3 Additional endpoint(s)

- ECOG response rate is defined as clinical complete response (cCR), pathological complete response (pCR) or partial response (PR), as measured by ultrasound according to ECOG response criteria (see [Appendix B](#)). The ECOG response (except pCR) will be assessed by investigator and collected in CRF.
- The proportion of participants achieving pCR after a 14-day treatment period. The pCR will be assessed by investigator and collected in CRF.
- PEPI risk score is the sum of the risk points derived from the pT stage, the pN stage, Ki67 levels and ER status of the surgical regimen. It will be calculated with the rules as defined in [Appendix C](#). PEPI score will be calculated for both RFS and BCSS based scale.
- Complete cell cycle arrest (CCCA) is a marker of reduced cellular proliferation, is defined as a Ki67 $\leq 2.7\%$ at D15 on central assessment.
- The proportion of participants with post-treatment Ki67 $< 10\%$.
- Additional protein expression assessments (eg, Ki67) by using digital image-based method.

2.1.4 Safety endpoints

The safety analysis will be based on the reported adverse events (AEs) and other safety information, such as clinical laboratory data, vital signs, weight, electrocardiogram (ECG) and ECOG PS.

Observation period

The observation period starts from the time when the patient gives informed consent and is divided into 3 periods:

- The pre-treatment period is defined as the time from when the participants give informed consent to the first administration of the IMP.
- The on-treatment period is defined as the time from the first dose of IMP up to last dose of IMP.
- The post-treatment safety follow-up period is defined as the time from last administration of the IMP to the last administration of the IMP +30 day

2.1.4.1 Adverse events variables

AEs (including serious adverse events [SAEs] and AEs of special interest [AESI]) will be collected from the time of signed informed consent until the end of study. In addition, All SAEs, non-serious AEs of special interest (as defined in [Section 2.1.4.1](#)), and non-serious AEs related to IMP still ongoing at time of study treatment discontinuation will be followed until resolution or stabilization.

Adverse event observation period

- Pretreatment AEs are defined as any AE occurring during the pretreatment period.
- Treatment-emergent AEs (TEAEs) are defined as AEs that develop, worsen (according to the Investigator's opinion), or become serious during
 - on treatment period (from first dose of IMP to last dose of IMP), or
 - on treatment and post-treatment period (from first dose of IMP to last dose of IMP +30 days)

Analysis will be performed for both analysis periods (see [Section 2.4.6.1](#))

- All AEs (including SAEs and AESI) will be graded according to National cancer institute common terminology for adverse events (NCI-CTCAE) v5.0 and coded to a lower-level term (LLT), preferred term (PT), high-level term (HLT), high-level group term (HLGT), and associated primary system organ class (SOC) using the version of MedDRA currently in effect at Sanofi at the time of database lock.

Adverse events of special interest

Specific analyses will be performed for the following AEs (see [Section 2.4.6.1](#)):

- Pregnancy occurring in a female participant entered in the clinical trial.
- Symptomatic overdose (serious or nonserious) with IMP
- Increase in alanine transaminase (ALT) \geq Grade 2
- Photosensitivity reaction

2.1.4.2 Deaths

A listing of on-study deaths (if any) will be provided.

2.1.4.3 Laboratory safety variables

Clinical laboratory data consists of blood analysis including hematology and biochemistry. Clinical laboratory values will be converted into standard international units that will be used in all listings and tables.

For laboratory safety variables, parameters measured on the day of the first study treatment intake will be considered as part of the baseline measurements.

For laboratory safety variables, the treatment period will start at first study treatment intake +1 day.

The laboratory safety parameters will be classified as follows:

- Hematology
 - **Red blood cells, platelets, and white blood cells:** platelet count, red blood cell (RBC) count, hemoglobin, hematocrit, white blood cell with differential: neutrophils, lymphocytes, monocytes, eosinophils, and basophils.
 - **Coagulation:** prothrombin time (PT) and international normalized ratio (INR).
- Biochemistry
 - **Metabolism:** fasting glucose, total protein.
 - **Electrolytes:** potassium, sodium, calcium.
 - **Renal function:** creatinine, blood urea nitrogen (BUN), urea, eGFR
 - **Liver parameters:** alanine aminotransferase (ALT), aspartate aminotransferase (AST), alkaline phosphatase, total and direct bilirubin.
- Hormone:
 - **Follicle-stimulating hormone** (for women with non-childbearing potential)

2.1.4.4 Vital signs variables

Vital signs include: pulse rate, systolic and diastolic blood pressure, weight, temperature and ECOG PS (0, 1, 2, 3, 4, 5).

For vital signs, parameters measured on the day of the first study treatment intake will be considered as part of the baseline measurements.

For vital signs, the treatment period will start at first study treatment intake +1 day.

For a given parameter, a patient will be considered as evaluable if at least one measure of this parameter is available during the on-treatment period.

2.1.4.5 Electrocardiogram variable

Triplicate electrocardiogram assessments will be described as normal or abnormal by central reading at pre-dose on Day 1 and at pre-dose and 3h post-dose on Day 14.

Single 12-lead ECGs will be recorded at screening by local assessment and investigator's opinion (normal/abnormal) will be reported.

The following parameters will be assessed/derived and provided for statistical analysis:

- PR (in ms)
- QRS (in ms)
- QT (in ms)
- Mean RR (in ms)
- QTcB (in ms) = $QT \cdot RR^{-0.50}$
- QTcF (in ms) = $QT \cdot RR^{-0.33}$
- Heart rate (in bpm) = $60/RR$ with RR in seconds

In case of triplicates assessments, only the mean of the triplicate will be presented. All parameters will be analyzed as raw data and absolute change from baseline (raw value at visit X - baseline value). In addition, for the abnormalities analyses and descriptive statistics, PR and QRS will be also analyzed as percent change from baseline ($100 \times [\text{raw value at visit X} - \text{baseline value}] / \text{baseline value}$). Semi-automatic reading from core lab of these quantitative parameters will be used for concentration-ECG analyses.

2.1.5 Pharmacokinetic variables

SAR439859 plasma concentrations will be determined at the predefined time point according to the SoA presented in Section 1.3 of the protocol.

In addition, population PK approaches might be used to calculate individual PK parameters estimates. The population PK analysis, if any, will be described in a separate report.

PK concentrations (and potentially PK parameter estimates) will be used to conduct an exploratory PK/PD relationship analysis of SAR439859 with pharmacodynamics (eg, Ki67) and/or safety (eg, triplicate ECG parameters, incidence of AEs).

2.1.6 Pharmacodynamic variables

2.1.6.1 Mutational profiling in circulating free DNA

Genomic analyses on circulating cell-free DNA (cfDNA) isolated from plasma samples will be performed in this study at baseline. The mutational status of a panel of 77 cancer driver genes (Roche AVENIO panel) will be determined by next generation sequencing (NGS) technology. Different types of genomic aberrations will be investigated such as single nucleotide variants,

indels, abnormal copy number variants or fusion genes. For both single nucleotide variants and indels, the type of mutation (missense, frameshift, inframe, ...), the mutant allele frequency (%) and the mutant concentration (ie, the number of mutant molecules per mL plasma) will be provided.

In addition, saliva samples will be collected pre-treatment as a source of normal reference DNA for comparison with the cfDNA but also with the tumor-derived DNA (see [Section 2.1.6.2](#)) data. Sequencing may be performed on the DNA from the saliva sample. In the event of technical issues affecting the sample, a replacement genetic saliva DNA sample may be requested from the participant.

2.1.6.2 Tumor biopsy

Determination of tumor characteristics (HER2 status by IHC or FISH, ER by IHC, Ki67 by IHC, etc) on the diagnostic biopsy specimen based on local laboratory results serves for participant selection.

Biopsy samples collected at screening and after a 14-day treatment period will be centrally examined for Ki67, DNA mutation analysis, RNA expression analysis, and protein analysis (eg, ER, PgR, BCL2, Cyclin D1) in central laboratory. Ki67 index will be recorded independently by 2 histopathologists blinded to treatment allocation. For the assessment of agreement in Ki67 measurements, see [Section 2.4.5.1.1](#). Ki67, ER, PgR, BCL-2 will also be collected by digital image-based method.

Genome-wide transcriptome sequencing of ribonucleic acid (RNA) isolated from tumor biopsies will be performed at screening and after a 14-day treatment period by measuring the relative abundances of the RNA transcripts through RNA sequencing. The ER activation score related to ER degradation will be derived from these RNAseq data. Other gene signatures (such as PAM50), immune cell abundances or pathways may be also explored from these data.

Finally, whole exome sequencing from tumor biopsies will be also performed at screening to highlight genomic aberrations directly from the tumor. A focus will be done on a predefined cancer research list containing around 1600 genes. As for mutational profiling from cfDNA, different types of genomic aberrations will be investigated such as single nucleotide variants, indels, abnormal copy number variants or fusion genes. For both single nucleotide variants and indels, the type of mutation (missense, frameshift, inframe, ...) and the mutant allele frequency (%) will be provided. The saliva samples will be used to differentiate somatic from non-somatic mutations. The tumor mutational burden score and the microsatellite instability will be also obtained from these data.

2.1.7 Further therapy after discontinuation of investigational medicinal product administration during the study

Further therapies after discontinuation of IMP include further anti-cancer therapy, surgery and radiotherapy.

2.2 DISPOSITION OF PATIENTS

Screened patients are defined as any patients who signed the study informed consent.

Randomized patient consists of all participants from the enrolled population and for whom there is a confirmation of successful allocation of a randomization number by IRT. This population is also referred as the intent-to-treat (ITT) population defined in [Section 2.3.1](#).

For patient study status, the total number of patients for each one of the following categories will be presented in the clinical study report (CSR) using a flow-chart diagram or a summary table:

- Screened patients
- Nonrandomized but treated patients
- Randomized patients
- Randomized but not treated patients
- Randomized and treated patients
- Patients who completed treatment
- Patients who discontinued study treatment and reasons for permanent discontinuation
- Patients who completed study.
- Patients who did not complete the study period and reasons for study discontinuation
- Patient still on treatment (interim analysis only)

Number of screened patients, number of screen failure patients and reasons for screen failure will be summarized in a separated table. In addition, number and percentage of screened patients by country and sites will be presented.

For all categories of patients (except for the screened and nonrandomized category) percentages will be calculated using the number of patients in randomized population as the denominator.

All critical or major deviations potentially impacting efficacy analyses, randomization, and drug-dispensing irregularities, and other major or critical deviations will be summarized in tables giving numbers and percentages of deviations by treatment group.

Additionally, the following analysis populations will be summarized in a table by number of patients on the randomized population:

- Intent-to-treat population
- Modified ITT (mITT) population
- Per-protocol (PP) population
- Safety population
- Pharmacokinetic-evaluable population

Definition of study populations are provided in [Section 2.3](#).

2.2.1 Randomization and drug dispensing irregularities

Randomization and drug-dispensing irregularities occur whenever:

- A randomization is not in accordance with the protocol-defined randomization method, such as a) an ineligible patient is randomized, b) a patient is randomized twice,
OR
- A patient is dispensed an IMP kit not allocated by the protocol-defined randomization, such as a) a patient at any time in the study is dispensed a different treatment kit than as randomized (which may or may not contain the correct-as-randomized IMP), or b) a nonrandomized patient is treated with IMP reserved for randomized patients.

Randomization and drug-dispensing irregularities will be monitored throughout the study and reviewed on an ongoing basis.

All randomization and drug-dispensing irregularities will be documented in the clinical study report. If the number of irregularities is large enough to make a tabular summary useful, the irregularities will be categorized and summarized among randomized patients (number and percentages). Nonrandomized, treated patients will be described separately.

Randomization and drug-dispensing irregularities to be prospectively identified include but are not limited to:

- Kit dispensation without IRT transaction
- Erroneous kit dispensation
- Kit not available
- Randomization by error
- Patient randomized twice

2.3 ANALYSIS POPULATIONS

Patients treated without being randomized will not be considered randomized and will not be included in any efficacy population.

The randomized population is defined in [Section 2.2](#).

For any patient randomized more than once, only the data associated with the first randomization will be used in any analysis population. The safety experience associated with any later randomization will be assessed separately.

The safety experience of patients treated and not randomized will be reported separately, and these patients will not be in the safety population.

2.3.1 Intent-to-treat (ITT) population

ITT population is defined as all participants from the enrolled population and for whom there is a confirmation of successful allocation of a randomization number by IRT. Participants will be analyzed according to the treatment arm assigned at randomization. This population will be used for analysis of baseline parameters.

2.3.2 Modified ITT (mITT) population

mITT population is defined as all participants from the ITT population who have taken at least one drug, and who have both baseline and post treatment available biopsies with Ki67 values. This is the primary analysis population for all efficacy and pharmacodynamic parameters.

2.3.3 Per-protocol (PP) population

PP population is defined as all participants from the mITT population without relevant deviation(s), which could affect the evaluation of the study drug on the primary endpoint. PP population will be used for sensitivity analysis of the primary endpoint.

Major or critical deviations leading to exclusion from the per-protocol population is defined as follows:

- **Informed consent procedure:**
 - Patient does not sign study informed consent or informed consent is signed after study procedure
- **Inclusion/exclusion criteria:**
 - Patient without histological and cytological proven diagnosis of invasive breast adenocarcinoma
 - The localized breast cancer is not eligible for upfront breast conservative surgery or upfront mastectomy
 - Patient is not postmenopausal as per age and criteria defined in the protocol
 - The breast tumor size is less than 10 mm in short axis measured by ultrasound
 - Patient doesn't have a primary tumor positive in ER or non-overexpressing HER2 per protocol definition
 - Ki67 level is lower than 15% at diagnosis from immunohistochemistry of the tumor based on local laboratory results
 - Ki67 level is lower than 15% at baseline based on central laboratory results
 - Prior anti-cancer treatment was completed <1 year prior to inclusion into this trial
 - Patient is not female
 - Recent use of hormone replacement therapy (last dose \leq 30 days prior to randomization)

- **Concomitant medications/therapy**
 - Protocol prohibited therapy/medication/vaccine administered
- **IMP management:**
 - Patient receives ≤ 10 days or ≥ 16 days of the IMP treatment
- **Randomization procedure:**
 - IMP dispensed without Randomization
 - IMP actually dispensed to the subject is different from the IMP allocated

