Viral serologies	X						Viral serologies include hepatitis A antigen or IgM hepatitis A antibody, HBs antigen or hepatitis B viral DNA, hepatitis C antibody or quantitative hepatitis C viral (HCV) ribonucleic acid (RNA).
Single 12-lead ECG	X						See Section 8.2.3 for details.
Triplicate ECG		X		X			Electronic records of triplicate ECG are required at pre-dose on D1 and at pre-dose and 3h post-dose on D14. See Section 8.2.3 for details.
Vital signs	X	(X)	X	X			These assessments will be repeated within 1 day prior to the first dosing of IMP if abnormal or if screening assessment >7 days of D1. See Section 8.2.2 for details.
Patient diary distribution		X					
Patient diary review			X	X			
Amcenestant administration 400 mg QD		Continuous once a day (QD)					Study treatment should be taken in the morning. Study treatment duration is planned for 14 days, and should not exceed 14 days. IMP will be dispensed at the study site visits on D1. On D1 and D14, IMP will be taken on-site after fasting tests and pre-dose assessment. See Section 6.1 for details.
Amcenestant administration 200 mg QD		Continuous once a day (QD)					
Letrozole administration		Continuous once a day (QD)					

Procedure ^a	Screening	Treatment Period (14 days)			Surgery ^c	Post treatment safety follow-up period	Notes
	up to 14 days before randomization	D1 ^b	D7 (±2)	D14	D15 (+1)	30 (±7) days after last IMP intake	
Tumor Biopsy ^d	X				X		Participant selection is based on the biopsy at diagnosis analyzed in a local lab. A new core-cut biopsy (baseline sample) should be performed prior to the first dosing of IMP, as well as a core-cut biopsy from surgery specimen or new core-cut biopsy after the last IMP intake for study purpose. Alternatively, tissue from the diagnostic biopsy may be used for the baseline sample if certain criteria are fulfilled. Baseline and post-treatment biopsy will be centrally examined. See Section 8.6.1 for details.
Tumor size by ultrasound	X			X			Measurement of tumor size using ultrasound at screening (baseline) and on D14. At screening, tumor size assessed by ultrasound will also be used for inclusion criteria. See Section 8.1.2 for details.

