5.1 INCLUSION CRITERIA

Participants are eligible to be included in the study only if all of the following criteria apply (in case bilateral breast cancer is diagnosed at the same time, only one location as per Investigator judgment will be selected for all selection and assessment criteria):

Age

- I 01. Participant must be older than 18 years of age inclusive, or country's legal age of majority if the legal adult age is >18 years old at the time of signing the informed consent

Type of participant and disease characteristics

- I 02. Patients with histological or cytological proven diagnosis of invasive breast adenocarcinoma
- I 03. Localized breast cancer eligible for upfront breast conservative surgery or upfront mastectomy: Stage I, Stage II or operable Stage III (excludes T4) (*AJCC Cancer Staging Manual 8th edition 2017*; [15])
- I 04. Participants must be postmenopausal women as defined by one of the following:
- With spontaneous cessation of menses >12 months prior to randomization.
 - Or who have received hormonal replacement therapy but have discontinued this treatment AND have FSH level in the postmenopausal range according to institutional standards (or >34.4 IU/L if institutional range is not available) prior to randomization. (Note: serial FSH measurements are required to confirm postmenopausal status in participants who are not using hormonal replacement therapy and in the absence of amenorrhea >12 months.)
 - Or with status post bilateral surgical oophorectomy.
 - Or post bilateral ovarian ablation through pelvic radiotherapy.
- I 05. A breast tumor size of at least 10 mm in greatest dimension measured by ultrasound
- I 06. Primary tumor must be positive:
- ER ($\geq 1\%$ tumor cell staining by IHC)
 - HER2 non-overexpressing by IHC (0, 1+) or in situ hybridization-negative based on single-probe average HER2 copy number <4.0 signals/cell or dual-probe HER2/centromeric probe for chromosome 17 (CEP17) ratio <2 with an average HER2 copy number <4.0 signals/cell (as per the American Society of Clinical Oncology guidelines).

I 07. Ki67 level of at least 15% at diagnosis from immunohistochemistry of the tumor based on local laboratory results

I 08. ECOG performance status 0-1

Weight

I 09. Not Applicable

Sex

I 10. Female

Informed Consent

I 11. Capable of giving signed informed consent which includes compliance with the requirements and restrictions listed in the informed consent form (ICF) and in this protocol.

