1 OVERVIEW AND INVESTIGATIONAL PLAN

1.1 STUDY DESIGN

This is an international, prospective, open-label, Phase 2 randomized study of 2-week preoperative treatment in ER positive, HER2 negative invasive primary breast cancer.

After a screening phase of up to 14 days, postmenopausal women with early breast cancer will be randomly (1:1:1) assigned to one of the following treatment arms: amcnestrant 400 mg QD, amcnestrant 200 mg QD or letrozole 2.5 mg QD. Patients will be treated for 14 days. The surgery date should be fixed before randomization. The surgery is to be performed 1 (+1) day after the last dose of study treatment.

Approximately 126 patients will be randomized such that 120 evaluable participants are reached. A total of 40 evaluable participants per treatment arm are expected.

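### Two per-protocol exclusion rules in SAP 2.3.3 use and/or differently from I02 and I06; in its ordinary reading the ER/HER2 rule keeps patients who fail only one of the two criteria

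*SAP*

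**What the plan says.** **Eligibility.** Protocol 5.1 opens with the rule that "Participants are eligible to be included in the study only if all of the following criteria apply". I02 admits "Patients with histological or cytological proven diagnosis of invasive breast adenocarcinoma", so either form of proof is enough. I06 begins "Primary tumor must be positive" and then lists two items: ER staining in at least 1% of tumor cells, and HER2 non-overexpression by IHC or a negative in situ hybridization (ISH) result. No connective is printed between the two items. That both are required follows from the opening rule and from the disease under study, which SAP 1.1 gives as "ER positive, HER2 negative invasive primary breast cancer".

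**PP exclusions.** Protocol 9.3 (Table 4) leaves the detail of relevant deviations to the SAP. SAP 2.3.3 then gives a list that it presents as the definition. Two entries matter here:

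- for I02: "Patient without histological and cytological proven diagnosis of invasive breast adenocarcinoma"
- for I06: "Patient doesn't have a primary tumor positive in ER or non-overexpressing HER2 per protocol definition"

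**Use of PP.** SAP 2.4.5.1.3 repeats the primary analysis on PP as a sensitivity analysis. For the secondary endpoints a PP repeat is optional in SAP 2.4.5.2, while Protocol 9.4.1 plans one for the endpoint of a Ki67 decrease of at least 50%.

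**The concern.** The SAP has *and* where I02 has *or*, and *or* where I06 needs both parts. In each entry the negation stands in front of the whole phrase, so the connective decides who is removed.

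The PP set is meant to show whether the primary result holds in patients without deviations that bear on the drug's effect. A patient whose tumor is outside the ER-positive, HER2-negative population is one that such a set should leave out. If the ER/HER2 rule is followed as it reads, some of these patients remain. If the histology rule is followed to the letter, eligible patients are removed. Because the protocol hands the definition to the SAP, this wording is what a programmer would work from.

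**Working it through.** There is no figure in the plan to reproduce; the check is one of logic. For each criterion, take all four combinations of its two parts and compare the patients the SAP rule removes with those who fail the protocol criterion. Two readings are tried:

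- **Whole-phrase**: the negation applies to the combined phrase.
- **Distributed**: the negation applies to each part separately.

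**ER/HER2 rule against I06.** Let E = ER positive and N = HER2 non-overexpressing or ISH-negative. A patient should be removed if not (E and N).

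| E | N | Meets I06 | Should be removed | Whole-phrase: not (E or N) | Distributed: not E, or not N |
|---|---|---|---|---|---|
| yes | yes | yes | no | no | no |
| yes | no | no | yes | **no** | yes |
| no | yes | no | yes | **no** | yes |
| no | no | no | yes | yes | yes |

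The whole-phrase reading agrees with the protocol in 2 of 4 rows. Of the three ways to violate I06 it removes one (failing both parts) and keeps two. The distributed reading agrees in 4 of 4.

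**Histology rule against I02.** Let H = histological proof and C = cytological proof. A patient should be removed if not (H or C).

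| H | C | Meets I02 | Should be removed | Whole-phrase: not (H and C) | Distributed: not H, and not C |
|---|---|---|---|---|---|
| yes | yes | yes | no | no | no |
| yes | no | yes | no | **yes** | no |
| no | yes | yes | no | **yes** | no |
| no | no | no | yes | yes | yes |

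The whole-phrase reading again agrees in 2 of 4 rows: it removes histology-only and cytology-only patients, both eligible. The distributed reading agrees in 4 of 4.

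**Which reading is natural?** The two rules differ here. Saying that someone does not have A or B ordinarily means that she has neither, which is the whole-phrase reading and the wrong one for I06. Saying that someone is without A and B can mean lacking the pair or lacking each, so the histology rule can be read either way.

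**Does the surrounding text settle it?** SAP 2.3.3 defines PP as mITT patients free of relevant deviations. That helps the histology rule: a patient with one form of proof meets I02, has no deviation, and should not be removed. It helps the ER/HER2 rule less. A patient who fails one part of I06 does have a deviation, but the list says which deviations lead to exclusion, and in its ordinary reading it names only the double failure. The rule's reference to the protocol definition fixes what ER and HER2 status mean; it does not clearly fix the connective.

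**The case against.** The best defense is that a sensible reader knows what was meant. With the negation distributed, both rules are exactly right, and that was probably the intent. The PP definition protects the histology-only patient, and the ER/HER2 rule sends the reader back to I06. Neither document gives the PP programming logic, so nothing shows that the derived flag is wrong. This largely stands for the histology rule. For the ER/HER2 rule it stands only in part, because the intended meaning is not the ordinary one. The list also cannot be assumed to mirror the current protocol: it applies the 10 mm tumor-size limit to the short axis, whereas I05 uses the greatest dimension.

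A second defense is that few patients should violate I06. ER and HER2 are determined locally for selection, and Protocol 5 does not permit waivers. Under SAP 2.2.1 the randomization of an ineligible patient is an irregularity to be documented in the study report, so such a patient might stay in PP but should not go unreported. This stands, and it limits the weight of the point.

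Stronger readings are tempting but not supported:

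- **That the histology rule could empty the PP set.** A reader might infer this because "Participant selection is based on the biopsy at diagnosis analyzed in a local lab" and the protocol does not require cytology as well. But no count of patients with one or both forms of proof is given. SAP 2.1.1 lists histology and histopathology type but no cytology variable, so a filter built on two separate flags is hypothetical. The PP definition also argues against it.
- **That retained violators would distort the Ki67 result.** The documents give no Ki67 response by HER2 or ER status. Being outside the target population is reason enough to exclude them from PP.

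**Conclusion.** The mismatch is real and worth correcting, at minor severity. The ER/HER2 rule is the main defect: in its ordinary reading it keeps two of the three patterns that violate I06. The histology rule is ambiguous, and its context points to the right reading.

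The reach is limited to the PP repeats of the primary analysis and of any secondary endpoint. The primary analysis on mITT (SAP 2.3.2 and 2.4.5.1.1) does not use these rules. SAP 2.4 drops hypothesis testing on the primary endpoint and treats confidence intervals as descriptive, so no test result depends on the PP set. The number of patients affected cannot be stated, because the documents give neither the number with a single form of proof nor the number with an ER or HER2 violation.

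The conclusion assumes that I06 requires both of its parts, as the opening rule of Protocol 5.1 and the study population indicate, and that the list in SAP 2.3.3 is the operative definition.

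**What to change.** In SAP 2.3.3, replace the two entries with wording that has one meaning:

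- *Primary tumor is not ER positive, or is not HER2 non-overexpressing/ISH-negative, per protocol I06.*
- *Patient with neither histological nor cytological proof of invasive breast adenocarcinoma.*

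Before database lock, confirm that the programmed PP flags follow I02 and I06, using the two four-row tables above as test cases.

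The cost is two lines of SAP text and a short check of the derivation. No new data are needed. Programming changes only if the check shows that a flag follows the whole-phrase reading.
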